# 7.11 Lung Function (Spirometry)

Subjects will undergo lung function testing at Screening to affirm eligibility (FEV1, FEV1:FVC ratio) and as a safety endpoint (FEV1, FVC, FEV1:FVC ratio, and forced expiratory flow (FEF)25-75%). For *my*bluTM and continue-smoking arms, spirometry will also be performed at the discharge from the study (Day 57) or upon early termination.

Descriptive statistics will be reported for measured and percent of predicted spirometry parameters by product arm and time point. Unscheduled events or rechecks post randomization will not be included in summaries. Similarly early termination results will not be included in summaries.

Spirometry results will be listed by subject.

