4.2 Exclusion Criteria

Subjects may be excluded from the study if there is evidence of any of the following criteria during Screening or check-in for Test Visit 1, as applicable.

- 1. Has a history or presence of clinically significant gastrointestinal, renal, hepatic, neurologic, hematologic, endocrine, oncologic, urologic, pulmonary (especially bronchospastic diseases and asthma), immunologic, psychiatric, or cardiovascular disease, or any other condition that, in the opinion of the Investigator, would jeopardize the safety of the subject or impact the validity of the study results.
- 2. Has a clinically significant abnormal finding on the physical examination, medical history, vital signs, ECG, or clinical laboratory results, in the opinion of the Investigator.
- 3. Has a positive test for human immunodeficiency virus (HIV), hepatitis B surface antigen (HBsAg), or hepatitis C virus (HCV).
- 4. Has had an acute illness (e.g., upper respiratory infection, viral infection) requiring treatment within 14 days prior to Test Visit 1.

Page 41 CA22747_PROTOCOL AMENDMENT 3_24MAR2020

- 5. Has a fever (> 100.5°F) at Screening or check-in for Test Visit 1.
- 6. Has a body mass index (BMI) greater than 40.0 kg/m² or less than 18.0 kg/m² at Screening.
- 7. Has a history of drug or alcohol abuse within 24 months of Screening, as determined by the Investigator.
- 8. Has a systolic blood pressure < 90 mmHg or > 150 mmHg, diastolic blood pressure < 40 mmHg or > 95 mmHg, or heart rate < 40 bpm or > 99 bpm at Screening.
- 9. Has a post-bronchodilator forced expiratory volume in 1 second to forced vital capacity (FEV₁:FVC) ratio < 0.7 and FEV₁ < 80% of predicted at Screening.
- 10. Has a post-bronchodilator FEV_1 increase $\geq 12\%$ and ≥ 200 mL from pre- to post-bronchodilator at Screening.
- 11. Is allergic to propylene glycol or glycerin.
- 12. Has an estimated creatinine clearance < 70 mL/minute (using the Cockcroft-Gault equation) at Screening.
- 13. Has a positive urine drug or alcohol breath test at Screening or check-in for Test Visit 1.
- 14. If female, the subject is pregnant, lactating, or intends to become pregnant during the time period from Screening through the duration of the study.
- 15. Has taken medication for depression or asthma within 12 months of check-in for Test Visit 1.
- 16. Has used prescription anti-diabetic medication and/or insulin therapy within 12 months of check-in for Test Visit 1.

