7.6 Safety

All clinical safety data will be listed by subject and time point and summarized as described in the SAP.

All reported events captured in the database will be listed in by-subject data listings. However, only study product use-emergent AEs. A study product use-emergent AE is defined as an AE that is starting or worsening at the time of or after the first study product use on Day -2.

Frequencies of subjects with study product use-emergent AEs, regardless of relationship to study product will be summarized and sorted by system organ class. Frequencies of subjects

with study product use-emergent SAEs will be likewise summarized. Frequencies of study product use-emergent AEs will be summarized by severity and relationship to study product.

Changes in physical examinations (if any) will be described in the text of the final report.

All prior and concomitant medications recorded during the study will be listed by subject.

The following pre- and post-bronchodilator lung function variables will be summarized.

- Measured and percent of predicted FEV₁
- Measured and percent of predicted FVC
- Measured and percent of predicted FEV₁:FVC ratio
- Measured and percent of predicted FEF_{25-75%}

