# 7.5 Clinical Laboratory Tests (Serum Chemistry, Hematology, and Urinalysis)

Serum Chemistry, hematology, and urinalysis samples will be collected at screening and check-in (Day -2) for all product arms. For *my*bluTM and continue-smoking arms, the clinical laboratory tests will also be performed at the end of Period 1 (Day 29) and the discharge from the study (Day 57, Period 2) or upon early termination.

Descriptive statistics will be reported for numeric clinical data and change from baseline by product arm and time point. Rechecked values prior to randomization will be used in calculating summary statistics. Baseline is the last non-missing value including recheck and unscheduled event before randomization (usually on Day -2 Check-in). Normal ranges will be listed.

Out of normal range and clinically significant laboratory values will be listed by subject. Results that are indicated as CS by the PI will be listed in the table.

A urine cotinine test will be completed at Screening and Check-in (Day -2) for all product arms. For *my*bluTM and continue-smoking arms, the urine cotinine test will also be performed on the first day of each Test Visit.

Urine drug tests and alcohol breath tests will be completed at Screening and Check-in (Day -2) for all product arms.

For females, serum pregnancy tests will be completed at Screening and urine pregnancy tests will be completed at Check-in for all product arms. For *my*blu™ and continue-smoking arms, the urine pregnancy tests will also be performed on the first day of each Test Visit. Results for these tests will be listed as "Negative" or "Positive."

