# 7.7 Electrocardiogram

A single 12-lead electrocardiogram (ECG) will be recorded at Screening for all product arms. For *my*bluTM and continue-smoking arms, the ECG will also be performed at the discharge from the study (Day 57) or upon early termination. For JUUL arm, the ECG will be performed at Day 1 and upon early termination.

Descriptive statistics will be reported for ECG parameters by product arm and time point. Unscheduled events or rechecks post randomization will not be included in summaries. Similarly early termination results will not be included in summaries.

ECG results will be listed by subject.

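### Spirometry and ECG are summarised only by arm and time point, with no within-subject change from Screening to Day 57, although the SAP plans change from baseline for laboratory values and physiologic endpoints

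*SAP*

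**What the plan says.** **Timing.** Spirometry and ECG are both done at Screening. In the myblu and continue-smoking arms, SAP 7.11 then says "spirometry will also be performed at the discharge from the study (Day 57) or upon early termination", and SAP 7.7 says "the ECG will also be performed at the discharge from the study (Day 57) or upon early termination". JUUL subjects have an ECG at Screening and Day 1 and no end-of-use spirometry, so this point concerns the two main-study arms only.

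**Summary.** For spirometry: "Descriptive statistics will be reported for measured and percent of predicted spirometry parameters by product arm and time point". For ECG: "Descriptive statistics will be reported for ECG parameters by product arm and time point". Both sections leave out unscheduled and recheck values after randomization. SAP 7.11 then adds "Similarly early termination results will not be included in summaries", and 7.7 has the same rule. The introduction to SAP 7 says missing data are handled with reduced denominators. The outputs are Table 14.3.5.5 (ECG) and Table 14.3.5.6 (spirometry), both on the Safety population. No shell is shown for either.

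**Treatment of other measures.** SAP 7.5 plans change for laboratory values: "Descriptive statistics will be reported for numeric clinical data and change from baseline by product arm and time point". SAP 6.3.2 plans change from baseline for the physiologic assessments. SAP 6.7.2 compares those endpoints with continue-smoking on change, and the table list in SAP 9 covers FeNO, blood pressure and heart rate in this way.

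**Protocol.** Section 7.4 provides change values only where they are indicated. Section 7.6 does not indicate them for lung function, but it does name both bronchodilator states: "The following pre- and post-bronchodilator lung function variables will be summarized".

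**The concern.** Secondary objective 10 is to confirm safety over 56 days of use of an inhaled product. Lung disease is among the conditions the protocol screens out, with the wording "pulmonary (especially bronchospastic diseases and asthma" in exclusion criterion 1. Spirometry is the lung-function safety endpoint, and each main-study subject who finishes supplies a before-and-after pair. The planned tables do not use that pairing, for two reasons.

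- **The rows need not cover the same people.** The Screening row can include everyone in the Safety population. The Day 57 row holds only those who reached Day 57. Part of any difference between the rows can therefore reflect who stayed.
- **The spread shown is between people.** The SD at each time point reflects differences in body size, sex and age as well as any effect of use. Nothing in the table says how variable the change is, so a difference in means cannot be given an interval. The four myblu cohorts are also formed by preference (protocol 4.5), so these characteristics need not balance across products.

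At stake is how precisely the safety report can describe change in lung function, and whether spirometry and ECG get the same treatment as the laboratory values.

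**Working it through.** **The plan's own figure.** Protocol 7.1 powers only the primary biomarkers. For S-PMA, with a difference of 0.5 × 3348 = 1674 ng, SDs of 2370 and 1512, 29 per group and one-sided alpha 0.0125, a Welch t calculation gives 0.8106, as stated. This has no bearing on lung function. There is no FEV1 or ECG precision figure to reproduce.

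**Inputs for an illustration in FEV1.**

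- n = 29 per group, from protocol 7.1. This is the planned minimum completing Day 28; the number with Day 57 spirometry could differ.
- Between-subject SD 0.6-0.9 L: an assumption, not in the documents.
- Screening-to-Day 57 correlation r = 0.85-0.95: an assumption, not in the documents.

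**Precision of myblu (one cohort) minus continue-smoking.**

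1. On Day 57 values, the 95% half-width is 1.96 × SD × √(2/29).
   - SD 0.6: 0.309 L
   - SD 0.8: 0.412 L
   - SD 0.9: 0.463 L
2. On within-subject change, multiply by √(2(1 − r)).
   - SD 0.6, r 0.95: 0.309 × 0.316 = 0.098 L
   - SD 0.8, r 0.90: 0.412 × 0.447 = 0.184 L
   - SD 0.9, r 0.85: 0.463 × 0.548 = 0.254 L
3. A reader could subtract Screening from Day 57 means in each arm. With only the tabulated SDs and no correlation, the half-width would have to be taken as 1.96 × SD × √(4/29), which is 0.437 L for SD 0.6 and 0.655 L for SD 0.9. That is wider than step 1, even though the estimate itself may be sound.
4. Pooling myblu, 116 against 29, with SD 0.8 and r 0.90: 1.96 × 0.8 × √(1/116 + 1/29) = 0.33 L on Day 57 values, and 0.33 × 0.447 = 0.15 L on change.

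**Change of subjects between rows.** Suppose 43 are assigned to a cohort and 29 are measured at the end (both planning numbers in protocol 7.1). The mean then moves by (14/43) × the gap in FEV1 between leavers and stayers. For assumed gaps of 0.1, 0.2 and 0.3 L the shift is 0.033, 0.065 and 0.098 L, with no change in anyone.

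**SAP text against the laboratory shell.** SAP 7.5 promises change from baseline. The Table 14.3.5.1 shell, which Tables 14.3.5.2 and 14.3.5.3 follow, shows only time-point rows.

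**The case against.** The case on the other side is substantial.

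- **The tables hold more than means.** SAP 7 plans n, SD, median, minimum and maximum, and SAP 7.11 adds percent of predicted, which removes part of the variation due to sex, height and age. By-subject listings are planned for both measures. This stands: individual changes can be derived, and where the same subjects contribute, the difference of two means is the mean change. A reader might infer that a decline could not be seen at all. The documents do not support that. What is missing is the spread of the change, and a summary restricted to subjects with both values.
- **The documents set no threshold for decline.** A reader might take the 200 mL in exclusion criterion 10 as a notable loss of FEV1. It is a post-bronchodilator increase of at least 12% and at least 200 mL at Screening, used to exclude reversible airway disease. It says nothing about decline over 56 days.
- **The numbers rest on assumptions.** This stands. The SD, the correlation and the leaver gap are all assumed, and the calculation is in litres. Even on change the half-width reaches 0.25 L, so the paired summary is sharper without being decisive.
- **Objective 10 names no comparator, and FeNO and the Cough Questionnaire also address the airways.** Both are fair, and FeNO is compared with continue-smoking on change. FeNO does not measure FEV1 or FVC, however. Protocol 3.2 includes the continue-smoking arm to account for natural variation during a long study, which is the reason to show the contrast descriptively.
- **Mixing of pre- and post-bronchodilator values is not shown.** SAP 7.11 does not mention the split, so a reader might infer that the rows combine the two. Protocol 7.6 lists both, SAP 8 states alignment with the protocol, and the spirometry listing in Appendix 16.2.8.6 separates them. The split only needs stating.
- **Shells are illustrative.** SAP 10 says they may not reflect every aspect of the study, so the missing laboratory change rows are a point to tidy up.

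**Conclusion.** The point holds as a reporting gap. For the two main-study arms, the SAP plans no within-subject change for spirometry or ECG, while planning it for laboratory values and for blood pressure, heart rate and FeNO. Screening and Day 57 means can rest on different subjects, and no SD or interval of change is given for lung function.

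The documents alone do not give the size of the loss. Under the assumptions above, using change narrows the 95% half-width for one myblu cohort against continue-smoking from about 0.31-0.46 L to about 0.10-0.25 L. The ratio is √(2(1 − r)), so the gain depends on the correlation and exists whenever r exceeds 0.5. No corresponding figure is offered for ECG. The primary analysis is not affected, and no clinical rule is in question.

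**What to change.** 1. In SAP 7.11 and 7.7, and in Tables 14.3.5.5 and 14.3.5.6, add change from Screening to Day 57 among subjects with both values: n, mean, SD, median, minimum and maximum. Give it by product, for all myblu subjects pooled, and for continue-smoking.
2. Show spirometry separately before and after the bronchodilator, as protocol 7.6 lists.
3. For FEV1, FVC, FEV1:FVC and FEF25-75%, add the myblu minus continue-smoking difference in mean change with a 95% confidence interval, labelled descriptive and without a test.
4. Add the change rows that SAP 7.5 promises to the shells for Tables 14.3.5.1 to 14.3.5.3.

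The cost is SAP wording, programming and a few more table rows. No visit, procedure or subject is added. The paired rows will have a smaller n than the Screening row, so the existing time-point rows should stay beside them.

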#### 8. SUMMARY OF CHANGES FROM PROTOCOL-PLANNED ANALYSIS

The analyses described in this SAP are aligned with those analyses described in the protocol.

#### 9. SUMMARY TABLES AND FIGURES

Summary tables and figures are numbered following the International Conference on Harmonization (ICH) structure but may be renumbered as appropriate during the compilation of the tables and figures for the CSR. Note that all summary tables and figures will be generated using SAS® Version 9.4 or higher.

#### **Section 14 Summary Tables and Figures**

The following is a list of table and figure titles that will be included in Section 14 of the report. Tables and figures may be renumbered as appropriate during the compilation of the report.

# 14.1 Demographic Data Summary Tables

Table 14.1.1	Summary of Disposition (Safety, ITT, and PP Populations)
Table 14.1.2	Demographic Summary (Safety, ITT, and PP Populations)
Table 14.1.3	Smoking History Summary (Safety, ITT, and PP Populations)
Table 14.1.4	Summary of Disposition (PK Population)
Table 14.1.5	Demographic Summary (PK Population)
Table 14.1.6	Smoking History Summary (PK Population)

# 14.2 Study Product Use, Biomarkers, Physiologic Assessments, Pharmacokinetics and Questionnaires Data Summary Tables and Figures

#### **14.2.1 Product Use Tables**

111211 1104400	
Table 14.2.1.1	Summary of In-Clinic Number of my blu TM Pods Started by Product and Day (ITT)
Table 14.2.1.2	Summary of In-Clinic Number of my blu ™ Pods Started by Product and Day (PP 28/29)
Table 14.2.1.3	Summary of In-Clinic Number of my blu ™ Pods Started by Product and Day (PP 56/57)
Table 14.2.1.4	Summary of In-Clinic Product Weight Changes by Product and Day (ITT)
Table 14.2.1.5	Summary of In-Clinic Product Weight Changes by Product and Day (PP 28/29)
Table 14.2.1.6	Summary of In-Clinic Product Weights Changes by Product and Day (PP 56/57)
Table 14.2.1.7	Summary of In-Clinic Number of Cigarettes Smoked by Product and Day (ITT)
Table 14.2.1.8	Summary of In-Clinic Number of Cigarettes Smoked Started by Product and Day (PP 28/29)
Table 14.2.1.9	Summary of In-Clinic Number of Cigarettes Smoked by Product and Day (PP 56/57)
Table 14.2.1.10	Summary of Self-Reported Number of my blu TM Pods Started by Product and Day (ITT)
Table 14.2.1.11	Summary of Self-Reported Number of my blu TM Pods Started by Product and Day (PP 28/29)
Table 14.2.1.12	Summary of Self-Reported Number of my blu TM Pods Started by Product and Day (PP 56/57)
Table 14.2.1.13	Frequency of Self-Reported Number of Puffs Taken From $my$ blu TM product (>= 50) by Product and Day (ITT)
Table 14.2.1.14	Frequency of Self-Reported Number of Puffs Taken From my blu TM product (>= 50) by Product Day (PP 28/29)
Table 14.2.1.15	Frequency of Self-Reported Number of Puffs Taken From $my$ blu TM product (>= 50) by Product and Day (PP 56/57)

Nerudia Ltd.					
myblu E-cigarettes Clinical Study Report No. CA22747					
	Table 14.2.1.16	Summary of Self-Reported Number of Cigarettes Smoked by Product and Day (ITT)			
	Table 14.2.1.17	Summary of Self-Reported Number of Cigarettes Smoked by Product and Day (PP 28/29)			
	Table 14.2.1.18	Summary of Self-Reported Number of Cigarettes Smoked by Product and Day (PP 56/57)			
	Table 14.2.1.19	Summary of Self-Reported Product Use by Product and Product Use Period (ITT)			
	Table 14.2.1.20	Summary of Self-Reported Product Use by Product and Product Use Period (PP 28/29)			
	Table 14.2.1.21	Summary of Self-Reported Product Use by Product and Product Use Period (PP 56/57)			
	14.2.2 Biomark	er Tables			
	14.2.2.1 Blood C	COHb			
	Table 14.2.2.1.1.	Summary of Whole Blood COHb by Study Product and Study Day (ITT Population)			
	Table 14.2.2.1.1.	Summary of Whole Blood COHb Change From Baseline by Study Product and Study Day (ITT Population)			
	Table 14.2.2.1.1.	Summary of Whole Blood COHb Percent Change From Baseline by Study Product and Study Day (ITT Population)			
	Table 14.2.2.1.1.	Summary of Whole Blood COHb by Study Product and Study Day (PP Population)			
	Table 14.2.2.1.1.	Summary of Whole Blood COHb Change From Baseline by Study Product and Study Day (PP Population)			
	Table 14.2.2.1.1.	6 Summary of Whole Blood COHb Percent Change From Baseline by Study Product and Study Day (PP Population)			
	Table 14.2.2.1.2.	Statistical Comparison of Whole Blood COHb Change From Baseline Between my blu TM and Continuous Smoking by Study Day (ITT Population)			
	Table 14.2.2.1.2.	2 Statistical Comparison of Whole Blood COHb Change From Baseline Between my blu TM and Continuous Smoking by Study Day (PP Population)			
	Table 14.2.2.1.3.	Statistical Comparison of Whole Blood COHb Change From Baseline Between Day 28 and Day 56 in the my blu TM Groups (ITT Population)			

inical Study Report No. CA22/4/		
Table 14.2.2.1.3.2	Statistical Comparison of Whole Blood COHb Change From Baseline Between Day 28 and Day 56 in the my blu TM Groups (PP Day56/57 Population)	
Table 14.2.2.1.3.3	Statistical Comparison of Whole Blood COHb Change From Baseline Between Day 28 and Day 56 in the my blu TM Groups (PP Day56/57 Population – Sensitivity Analysis)	
Table 14.2.2.1.4.1	Statistical Comparison of Whole Blood COHb Change From Baseline Between my blu TM Groups by Study Day (ITT Population)	
Table 14.2.2.1.4.2	Statistical Comparison of Whole Blood COHb Change From Baseline Between my blu TM Groups by Study Day (PP Population)	
14.2.2.2 Urine NNA	L	
Table 14.2.2.2.1.1	Summary of Urine NNAL 24-hour Amount Excreted by Study Product and Study Day (ITT Population)	
Table 14.2.2.2.1.2	Summary of Urine NNAL Amount Excreted Change From Baseline by Study Product and Study Day (ITT Population)	
Table 14.2.2.2.1.3	Summary of Urine NNAL Amount Excreted Percent Change From Baseline by Study Product and Study Day (ITT Population)	
Table 14.2.2.2.1.4	Summary of Urine NNAL Adjusted for Urine Creatinine by Study Product and Study Day (ITT Population)	
Table 14.2.2.2.1.5	Summary of Urine NNAL Adjusted for Urine Creatinine Change From Baseline by Study Product and Study Day (ITT Population)	
Table 14.2.2.2.1.6	Summary of Urine NNAL Adjusted for Urine Creatinine Percent Change From Baseline by Study Product and Study Day (ITT Population)	
Table 14.2.2.2.1.7	Summary of Urine NNAL Amount Excreted by Study Product and Study Day (PP Population)	
Table 14.2.2.2.1.8	Summary of Urine NNAL Amount Excreted Change From Baseline by Study Product and Study Day (PP Population)	
Table 14.2.2.2.1.9	Summary of Urine NNAL Amount Excreted Percent Change From Baseline by Study Product and Study Day (PP Population)	

J -1	
Table 14.2.2.2.1.10	Summary of Urine NNAL Adjusted for Urine Creatinine by Study Product and Study Day (PP Population)
Table 14.2.2.2.1.11	Summary of Urine NNAL Adjusted for Urine Creatinine Change From Baseline by Study Product and Study Day (PP Population)
Table 14.2.2.2.1.12	Summary of Urine NNAL Adjusted for Urine Creatinine Percent Change From Baseline by Study Product and Study Day (PP Population)
Table 14.2.2.2.2.1	Statistical Comparison of Urine NNAL 24-hour Amount Excreted Change From Baseline Between my blu TM and Continuous Smoking by Study Day (ITT Population)
Table 14.2.2.2.2.2.2	Statistical Comparison of Urine NNAL 24-hour Amount Excreted Change From Baseline Between my blu TM and Continuous Smoking by Study Day (PP Day28/29 Population)
Table 14.2.2.2.2.3	Statistical Comparison of Urine NNAL 24-hour Amount Excreted Change From Baseline Between my blu TM and Continuous Smoking by Study Day (PP Day56/57 Population)
Table 14.2.2.2.2.4	Statistical Comparison of Urine NNAL 24-hour Amount Excreted Change From Baseline Between my blu TM and Continuous Smoking by Study Day (PP Day56/57 Population – Sensitivity Analysis)

#### 14.2.2.3 Urine 3-HPMA

*Tables 14.2.2.3.1.1 through 14.2.2.3.2.2.4 will be generated for Urine 3-HPMA similar to Urine NNAL.* 

#### 14.2.2.4 Urine S-PMA

Tables 14.2.2.4.1.1 through 14.2.2.4.2.24 will be generated for Urine S-PMA similar to Urine NNAL.

#### 14.2.2.5 Urine NNN

Tables 14.2.2.5.1.1 through 14.2.2.5.2.2., as applicable (ITT population only), will be generated for Urine NNN similar to Urine NNAL.

#### **14.2.2.6 Urine CEMA**

Tables 14.2.2.6.1.1 through 14.2.2.6.2.2, as applicable (ITT population only), will be generated for Urine CEMA similar to Urine NNAL.

